5.2.2 Exclusion Criteria

1. Any serious medical condition, laboratory abnormality, or psychiatric illness that would prevent the subject from signing the informed consent form.
2. Pregnant or breast feeding females. (Lactating females must agree not to breast feed while taking lenalidomide or azacitidine).
3. Any condition, including the presence of laboratory abnormalities, which places the subject at unacceptable risk if he/she were to participate in the study or confounds the ability to interpret data from the study.
4. Use of any experimental drug or therapy other than carfilzomib and pomalidomide within 28 days of treatment start on this protocol.
5. Neuropathy $>$ Grade 2
6. Known hypersensitivity to thalidomide, lenalidomide, azacitidine, or mannitol.
7. The development of erythema nodosum if characterized by a desquamating rash while taking thalidomide or lenalidomide drugs.
8. Concurrent use of other anti-cancer agents or treatment or concurrent radiation to the pelvis. Palliative radiation to areas outside the pelvis is allowed.
9. Previous inability to tolerate full-dose lenalidomide, adjusted to creatinine clearance (CrCl) according to Cockcroft-Gault at the time of previous lenalidomide treatment (25mg day 1-21 every 28 days if CrCl $\geq 60\text{mL/min}$, 10mg lenalidomide d1-21 every 28 days if CrCl $< 60\text{mL/min}$ but $\geq 30\text{mL/min}$, lenalidomide 15mg every 48 h d1-21 every 28 days if CrCl $< 30\text{mL/min}$ but not requiring dialysis, lenalidomide 5mg daily, day 1-21 every 28 days if CrCl $< 30\text{mL/min}$ and requiring dialysis).

5.3 Definition Relapsed Myeloma and Refractory Myeloma

A recent ASH/FDA panel has recommended to include clinical criteria to define relapsed myeloma and to separately analyze data for the relapsed as opposed to the refractory group of patients (56). In accordance with this consensus statement, International Myeloma Working Group diagnostic criteria (57), and the international uniform response criteria (58) the following definitions will be used:

5.3.1 Refractory Myeloma.

Biochemical or clinical evidence of loss of disease control within 90 days after the last therapy. Any of the following defines refractory myeloma:

1. Progressive disease (see 5.8.1) on prior therapy
2. Best response to prior therapy was stable disease (see under 7)
3. Progressive disease (see 5.8.1) within 90 days of the last therapy

5.3.2 Relapsed Myeloma.

Not fulfilling criteria for refractory disease and at least one biochemical **and** at least one clinical criterion fulfilled indicating recurrence of disease more than 90 days after the last therapy:

One or more biochemical criteria for recurrent disease:

An increase of 25% from lowest response value in any one or more of the following, verified on two consecutive measurements:

1. Serum M-component (absolute increase must be ≥ 0.5 g/100 ml) *
2. Urine M-component (absolute increase must be ≥ 200 mg per 24 h)
3. Only in patients without measurable serum and urine M-protein levels: the difference between involved and uninvolved FLC levels (absolute increase must be >100 mg/l)
4. Bone marrow plasma cell percentage (absolute % must be $\geq 10\%$)

AND one or more clinical criteria for recurrent disease:

Any of the following:

1. Definite development of new bone lesions or soft tissue plasmacytomas
2. Definite increase in the size of existing bone lesions or soft tissue plasmacytomas. A definite increase is defined as a 50% (and at least 1 cm) increase as measured serially by the sum of the products of the cross-diameters of each measurable lesion
3. Development of hypercalcemia (corrected serum calcium >11.5 mg / 100ml) that can be attributed solely to the plasma cell proliferative disorder
4. Decrease of hemoglobin by at least 2g/dL below the best independent value (without ESA or blood transfusion for at least 28 days) since the end of previous

therapy or new decrease in HgB below 10g/dL or to 2g/dL below the lower limit of normal

5. New increase in serum creatinine to $> 2\text{mg/dL}$, or increase by 2mg/dL attributed to myeloma progression

*: If the starting serum m-protein level is $\geq 5\text{g/dL}$ an absolute increase of $\geq 1\text{g/dL}$, verified on two consecutive measurements, is sufficient as a biochemical criterion for recurrent disease.

5.4 Visit Schedule and Assessments

Screening assessments and all on study scheduled visits and assessments are outlined in Section 2 Table of Study Assessments.

At treatment discontinuation, subjects will undergo off study evaluations per the Schedule of Assessments, Section 2. In addition, a safety assessment will be done approximately 28 days post the last dose of protocol therapy. Follow-Up contact with the subjects should occur at a minimum of every three months for three years from study entry.

5.5 Correlative Science

Azacitidine has been shown to reactivate expression of tumor suppressor genes silenced by DNA methylation of their promoters in multiple cell lines, animal experiments, and clinical trials, but so far this has not been demonstrated in myeloma cells of patients treated with azacitidine. Lenalidomide has pleiotropic effects that can include selective reactivation of SPARC in 5q- but not cytogenetically normal erythroid progenitors (59). The two drugs might therefore act in concert, reactivating tumor suppressor genes silenced in myeloma cells. With the proposed studies we will investigate baseline DNA methylation and gene expression of myeloma cells and if silenced tumor suppressor genes can be reactivated using the proposed regimen. Effects on normal CD34+ hematopoietic progenitors will be investigated as well.

5.5.1 Sample Handling and Processing

All samples obtained at the Cleveland Clinic will be picked up and processed by staff of [name] laboratory (R4-035) the same day they are obtained. The personnel obtaining the sample (bone marrow technicians and phlebotomists) will be given a sheet (appendix V, VI) specifying what tubes are to be used and who to page ([name]) upon sample acquisition.

Samples obtained at University Hospitals will be shipped by same-day courier service at room temperature to:

[name]

Cleveland Clinic Taussig Cancer Institute, R4-035

[name]

[name]

[contact]; [contact]; Email: [contact]

Please either page or email [name] when sample is shipped. Email: [contact]

Paging: [contact] – [name] followed by # sign – enter call back number followed by # sign

Bone marrow samples from University Hospitals will also be processed the same day by staff of [name] laboratory, peripheral blood samples may be stored at 4-8°C and processed the following day if the sample arrives late.

5.5.2 Bone Marrow Examinations

Two 20mL syringes, each pre-filled under sterile conditions with 2mL heparin will be used to obtain 40mL bone marrow aspirate on day 1 (or up to 7 days prior) of the first cycle and on day 1 of the second cycle, each time before drug administration. After isolation of mononuclear cells using the Ficoll™ method, CD34+ cells and CD138+ cells will be purified using 2 purification steps with Miltenyi columns followed by flow cytometric assessment of achieved purity. Samples of at least 70% purity will be used to assess DNA demethylation and mRNA reactivation. DNA and RNA of purified cells will be harvested using the Qiagen AllPrep DNA/RNA mini kit™, which allows for column-based isolation of DNA and RNA from the same sample. Isolated RNA and DNA will be stored at -80°C. Within 30 days (once a month) RNA samples will be transcribed into cDNA using Superscript III (Invitrogen™), then stored at -80°C until further analysis. The Illumina® HT12 array will be used to analyze global gene expression in CD138+ cells. DNA methylation profiling will be performed using the Illumina® HumanMethylation27 BeadChip array in CD138+ and CD34+ cells according to the manufacturer's instructions including bisulfite modification using Zymo™ kits. For approximately 10 selected sample genes, changes in expression after cycle one will be confirmed using real-time RT-PCR (TaqMan, Applied Biosystems™).

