Physical examination, vital signs, weight	X	X ¹	X	X	X	X		X		X	X	
ECOG performance status	X	X ¹	X	X	X	X		X		X	X	
Skeletal survey ²	X											
Bone marrow ³	X	X ¹				X						
ECG	X											
CBC with differential	X	X ¹	X	X	X	X	X	X	X	X	X	
Research blood sample (10mL EDTA, 10mL Heparin)	X	X	X	X	X	X		X				
Calculated creatinine clearance (by Cockcroft-Gault) ⁴	X	X ¹				X ⁴		X ⁴		X ⁴		
TSH ⁵	X ⁵	X ¹						X ⁵		X ⁵	X ⁵	
SPEP w m-spike, 24hr urine w m-spike, serum and urine immunofixation, serum quantitative immunoglobulins, serum free light chain assay, beta-2 microglobulin,	X	X ¹				X		X		X	X	
Complete metabolic panel	X	X ¹	X	X	X	X	X	X	X	X	X	
LDH, phosphorus, uric acid	X	X ¹										
Pregnancy testing ⁷	X ⁸	X ⁸	X ⁸	X ⁸	X ⁸	X ⁸		X ⁸		X ⁸	X ⁸	
Register patient into RevAssist® program ⁹	X ⁹											
Prescribe lenalidomide via RevAssist® ¹⁰		X ¹⁰				X ¹⁰		X ¹⁰		X ¹⁰		
Azacitidine administration		X ¹¹										
Dexamethasone prescription		X ¹²				X ¹²		X ¹²				
Response assessment ¹³						X		X		X	X	
Record adverse events ¹⁴		X	X	X	X			X		X	X ¹⁴	
Record concomitant therapies/procedures	X	X				X		X		X	X	
Obtain Follow-Up anti-cancer treatments												X
Obtain Follow-Up survival information												X

* Variations of ± 3 days of the scheduled visit are permitted.

If Physical examination, vital signs, weight and ECOG performance status were done within 7 days of Day 1, they do not need to be repeated at Study Day 1. An unscheduled visit can occur at any time during the study. Source must be maintained for these unscheduled visits. The date for the visit and any data generated must be recorded on the appropriate CRF. Source documents for these unscheduled visits must also be maintained.

Version: 07/16/2015

¹ If screening assessments were done within 7 days of Day 1, they do not need to be repeated at Study Day 1.

² A skeletal survey may be obtained up to 28 days before day 1, cycle 1. It will be repeated every 12 months or earlier if symptoms suggest bony progression.

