In MDS azacytidine at 75mg/m² d1-5 every 28 days or 50mg/m² d1-5 and 8-12 every 28 days was relatively well tolerated in combination with lenalidomide 5-10mg daily and showed promising activity with an overall response rate of 71% and a complete response rate of 41%, suggesting the two drugs can be combined synergistically without excess toxicity(46). The FDA approved regimen of azacitidine, 75mg/m² day 1-7 every 28 days for the treatment of MDS leads to maximal blood concentrations that, while lower than in the original studies, are still directly cytotoxic in vitro(47) which could limit the tumor suppressor gene reactivating function by inhibiting DNA duplication which is required for DNA demethylation. It furthermore likely contributes to side effects that make a treatment interruption of three weeks necessary to allow for recovery when the standard MDS schedule is used (75mg/m² d1-7 every 28 days). Unfortunately this also leads to DNA re-methylation before a new cycle begins (25, 48, 49). Furthermore, in diseases with a lower proliferative rate, like multiple myeloma, only a minority of cells would be expected to reactivate tumor suppressor genes if the drug was only given on one out of four weeks. In vitro, non-toxic single low doses of azacitidine (1µM) can reactivate tumor suppressor genes in myeloma cell lines for 3-7 days (unpublished observations). Doses higher than 2-5µM, depending on the cell type, can exert immediate toxicity likely related to nucleoside analogue properties of the drug. Pharmacokinetic data in humans suggest that a single dose of 50mg/m² subcutaneously reaches concentrations that should be sufficient for DNA demethylation but could cause classical nucleoside analogue toxicity in some patients (2.89µM +/- 1.35 µM SD), higher doses like 75mg/m² reach 4.88 µM +/- 1.4µM SD and thus almost certainly exert classic nucleoside analogue toxic effects (13). In this study we aim to avoid pronounced nucleoside analogue side effects while maximally exploiting DNA demethylating effects of azacitidine. We will therefore assess the safety of combination therapy with azacitidine given at low but increasing doses up to 50mg/m² twice a week, together with standard dose lenalidomide and low dose dexamethasone in relapsed or refractory myeloma patients in a phase I/II study with 10 additional patients enrolled at the highest tolerated low azacitidine dose to obtain an initial impression of efficacy and to evaluate whether this dose exerts the expected pharmacodynamic effects in myeloma cells before a larger phase II trial may be conducted.

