4.2.2 Secondary Endpoints

- Response will be determined monthly during the first 12 cycles and every two months thereafter with serum and 24hr urine protein electrophoresis, and as appropriate, supplemented by immunofixation, serum free light chain assay, and bone marrow examination. Response before high dose melphalan and autologous stem cell transplant will also be confirmed by two separate blood and 24 hr urine tests between the last dose of combination therapy and the first dose of the mobilizing agent.

- Plasma from peripheral blood draws will be used to quantify the activity of CDA using an HPLC method (see under 5.5.3)
- Progression-free survival will be measured from study entry to progression as defined by international response criteria (see under 5.9.1) or death of any cause, whichever comes first.
- Overall survival will be measured from study entry to death from any cause.
- CD34+ cell yield will be calculated based on flow cytometry of mononuclear cells harvested following stem cell mobilization. Time to neutrophil ($\geq 1,000/\text{mm}^3$) and platelet ($\geq 100,000/\text{mm}^3$) recovery will be counted from the day of stem cell infusion (=day 0)
- Promoter demethylation and gene reactivation will be measured at least at the HTLD / HTLD-CKD level using the Illumina® HumanMethylation27 BeadChip array on CD138 purified and CD34 purified cells obtained from bone marrow aspirates within 7 days before treatment start and at the end of cycle #1. RNA will be harvested from the same cell populations to confirm reactivation of selected genes identified on the array. Since the HTLD / HTLD-CKD is identified retrospectively DNA and RNA will be isolated from purified cell populations from all bone marrow aspirations before and after cycle #1.
- The RNA harvested from myeloma cells before and after the first cycle of therapy at the HTLD / HTLD-CKD level will furthermore be used to identify changes in global gene expression using the Illumina® HT12 array.

5 Investigational Plan

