5.6.2.3 Combination Therapy

Dosing Schedule for Patients with GFR \geq 60ml/min (Cockroft-Gault)

Dose level	Azacitidine (s.c.)* Starting day 1	Lenalidomide (p.o.) Starting day 1	Dexamethasone (p.o.)
------------	---------------------------------------	---------------------------------------	----------------------

1	30mg/m ² once a week ¹	25mg d1-21 every 28d ³	40mg p.o. once a week ⁴
2	40mg/m ² once a week ¹	25mg d1-21 every 28d ³	40mg p.o. once a week ⁴
3	30mg/m ² s.c. twice a week ²	25mg d1-21 every 28d ³	40mg p.o. once a week ⁴
4	40mg/m ² s.c. twice a week ²	25mg d1-21 every 28d ³	40mg p.o. once a week ⁴
5	50mg/m ² s.c. twice a week ²	25mg d1-21 every 28d ³	40mg p.o. once a week ⁴

* After highest tolerated low dose (HTLD) of azacitidine determination, azacitidine starting dose will be at the HTLD

Dosing Schedule for Patients with GFR 30-59ml/min (Cockcroft-Gault)

Dose level	Azacitidine (s.c.)* Starting day 1	Lenalidomide (p.o.) Starting day 1	Dexamethasone (p.o.)
-1	30mg/m ² s.c. twice a week ²	10mg d1-21 every 28d ³	40mg p.o. once a week ⁴
1	40mg/m ² s.c. twice a week ²	10mg d1-21 every 28d ³	40mg p.o. once a week ⁴
2	50mg/m ² s.c. twice a week ²	10mg d1-21 every 28d ³	40mg p.o. once a week ⁴

* After highest tolerated low dose (HTLD-CKD) of azacitidine determination, azacitidine starting dose will be at the HTLD-CKD

¹ Ideally, azacitidine is administered on the same day each week, but +/- up to two days is allowed, individual doses should be at least 5 days apart. Rotation of injection sites is obligatory.

² Azacitidine should be administered on the same days each week, +/- one day is allowed but there should be at least 48hrs between doses. The following schedules are recommended: Monday-Thursday, Monday-Friday, Tuesday-Friday, Tuesday-Saturday. Rotation of injection sites is obligatory

³: Lenalidomide dosing will be in the evening at approximately the same time each day. Prescriptions must be filled within 7 days. If a dose of lenalidomide is missed, it should be taken as soon as possible on the same day. If it is missed for the entire day, it should not be made up. Patients who take more than the prescribed dose of lenalidomide should be instructed to seek emergency medical care if needed and contact study staff immediately.

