5.7.4 Instructions for Initiation of a New Cycle

A new course of treatment may begin on the scheduled Day 1 of a new cycle if:

- The ANC is $\geq 1000/\text{mm}^3$ (G-CSF is allowed to achieve this threshold)
- The platelet count is $\geq 50,000/\text{mm}^3$ (During the first 4 cycles platelet transfusions are allowed to achieve this threshold)
- Any new drug-related neuropathy or rash other than injection site reaction that may have occurred has resolved to \leq grade 1 severity;
- Any bicarbonate decrease below 20mEq/L that may have occurred has resolved to baseline.
- Calculated creatinine clearance $\geq 30\text{ml}/\text{min}$ (by Cockroft-Gault), after 12 cycles on therapy, determining the creatinine clearance every 2 months will suffice
- Any other drug-related adverse events that may have occurred have resolved to \leq grade 2 severity. Physician discretion may be used in initiating the next cycle of treatment if the only toxicities that have not resolved to \leq grade 2 severity are dexamethasone-related toxicities.

If these conditions are not met on Day 1 of a new cycle, the subject will be evaluated weekly and a new cycle of treatment will not be initiated until the toxicity has resolved as described above. If criteria to initiate a new cycle are not met by 21 days after the planned start of a new cycle patients go off study. If a lenalidomide or azacitidine dose reduction was taken during the previous cycle, and the cycle was completed without requiring further dose modification, then the next cycle will start at the same reduced dose. **If lenalidomide and / or azacitidine dosing was omitted for the remainder of the previous cycle or if the new cycle is delayed due to toxicity newly encountered on the scheduled Day 1**, then the new cycle will be started with a one-level dose reduction of lenalidomide and/or azacitidine as appropriate. Dose reductions should generally be taken one drug at a time based on attribution of toxicity to one of the drugs unless otherwise indicated in Section 5.7.3.

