5.7.5 Instructions for Dose Modifications or Interruption During a Cycle

Table 5 outlines instructions for dose reductions of study drugs for specific toxicities. Study drugs may be temporarily or permanently dose reduced using doses outlined in table 1-4 or temporarily discontinued in other situations where their continued administration according to protocol is felt unsafe by the treating physician.

Table 5: Dose Modifications Azacitidine and Lenalidomide

NCI CTC Toxicity Grade	Dose Modification Instructions
Grade 3 neutropenia associated with fever (temperature $\geq 38.5^{\circ}$ C) or Grade 4 neutropenia	
 • Hold (interrupt) lenalidomide and, while on combination, also azacitidine dose. • Follow CBC weekly. • During combination therapy with lenalidomide and azacitidine: 
 ◦ If neutropenia has resolved to \leq grade 2 prior to Day 21 of the current cycle, restart azacitidine at the next lower dose level and continue lenalidomide at the same dose level if the patient's myeloma has not previously been refractory to lenalidomide, otherwise maintain azacitidine dose level and reduce lenalidomide by one dose level (if the patient is only on one of these drugs reduce its dose by one level) and continue treatment through the scheduled end of the cycle. Otherwise, omit treatment for the remainder of the cycle and reduce dose levels in the same way at the start of the next cycle. Omitted doses are not made up. ◦ If neutropenia is the only toxicity for which a dose reduction is required (no fever or other reason to reduce doses), G-CSF should be considered instead of a dose reduction. • During maintenance therapy with lenalidomide: 
 ◦ If neutropenia has resolved to \leq grade 2 prior to Day 21 of the current cycle, restart lenalidomide at the next lower dose level, and continue through the scheduled end of the cycle. Otherwise, omit lenalidomide for the remainder of the cycle and reduce lenalidomide by 1 dose level at the start of the next cycle. Omitted doses are not made up.

Table 5: Dose Modifications Azacitidine and Lenalidomide

NCI CTC Toxicity Grade	Dose Modification Instructions

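### The second research marrow is tied to the start of cycle 2 rather than the end of cycle 1, so a delay or omitted azacitidine can lengthen the drug-free interval by weeks, and the analysis does not account for it

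*Combined protocol and SAP*

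**What the plan says.** The endpoint text (Synopsis and 4.2.2) bases promoter methylation and gene reactivation on CD138- and CD34-purified cells "obtained from bone marrow aspirates within 7 days before treatment start and at the end of cycle #1". The procedure in 5.5.2 takes the second sample "on day 1 of the second cycle, each time before drug administration", and the Section 2 schedule marks it under cycle 2 day 1, with the general footnote that "Variations of ± 3 days of the scheduled visit are permitted". The schedule marks no marrow at discontinuation. Neither text refers to the last azacitidine dose.

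Two provisions can separate that dose from the marrow:

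- **Delay of cycle 2 (5.7.4).** Patients are re-evaluated weekly until the start criteria are met. "If criteria to initiate a new cycle are not met by 21 days after the planned start of a new cycle patients go off study".
- **Omission of azacitidine (5.7.5, Table 5).** For grade 4 or febrile grade 3 neutropenia, both drugs are held. If the neutropenia resolves before day 21, treatment resumes through the scheduled end of the cycle. "Otherwise, omit treatment for the remainder of the cycle". Several other toxicities have similar rules.

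On the biology, 3.3 states that a single low in vitro dose "can reactivate tumor suppressor genes in myeloma cell lines for 3-7 days". Of the three-week break in the standard MDS schedule it says: "Unfortunately this also leads to DNA re-methylation before a new cycle begins".

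The analysis in 5.5.4 counts genes whose methylation score changes significantly or by at least 0.2. The only pre/post difference it undertakes to account for is sample purity.

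**The concern.** Demethylation, gene reactivation and global expression after cycle 1 are secondary objectives. The Synopsis and 3.3 also give the pharmacodynamic effect in myeloma cells as one of two reasons for the ten-patient extension. The answer depends on how long after drug exposure the marrow is taken, and the plan lets that interval vary with toxicity and recovery.

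The rationale for continuous low dosing is partly that a long drug-free gap lets methylation return. A sampling rule that follows the start of cycle 2 can recreate such a gap in some patients. If their pairs show little change, the analysis has no means of separating an inactive dose from a late sample. Patients who never meet the cycle 2 criteria have no scheduled second research marrow, although the endpoint text implies one.

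**Working it through.** **Inputs**

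- Cycle length is 28 days, so an on-time cycle 2 day 1 is study day 29. The latest permitted start is 29 + 21 = day 50 (5.7.4).
- Twice-weekly dosing (5.6.2.3): "The following schedules are recommended: Monday-Thursday, Monday-Friday, Tuesday-Friday, Tuesday-Saturday". Counting the first dose as day 1, the doses fall on days 1, 4, 8, 11, 15, 18, 22, 25 or on days 1, 5, 8, 12, 15, 19, 22, 26. The last planned dose is therefore day 25 or 26.
- Weekly dosing (levels 1 and 2): last planned dose on day 22.
- Patients at the HTLD / HTLD-CKD: 16-22 (10.2.3). This reproduces as 6 + 10 = 16 and 6 + 6 + 10 = 22.

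The documents state no interval from last dose to marrow, so there is no figure of theirs to reproduce for it.

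**Formula:** interval = marrow day − day of last azacitidine dose.

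**Twice-weekly dosing, marrow on cycle 2 day 1**

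| Course | Last dose (day) | Marrow (day) | Interval (days) |
|---|---|---|---|
| Full dosing, cycle 2 on time | 25 or 26 | 29 | 4 or 3 |
| Held on day 8, restarted on day 15, on time | 25 or 26 | 29 | 4 or 3 |
| Full dosing, 7-day delay | 25 or 26 | 36 | 11 or 10 |
| Full dosing, 14-day delay | 25 or 26 | 43 | 18 or 17 |
| Full dosing, 21-day delay | 25 or 26 | 50 | 25 or 24 |
| Held from day 22, rest omitted, on time | 18 or 19 | 29 | 11 or 10 |
| Held from day 15, rest omitted, on time | 11 or 12 | 29 | 18 or 17 |
| Held from day 8, rest omitted, on time | 4 or 5 | 29 | 25 or 24 |
| Held from day 15, rest omitted, 21-day delay | 11 or 12 | 50 | 39 or 38 |
| Held from day 8, rest omitted, 21-day delay | 4 or 5 | 50 | 46 or 45 |

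For weekly dosing the interval is 29 − 22 = 7 days on time and 50 − 22 = 28 days after a 21-day delay.

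**Effect of the visit window.** With ±3 days, an on-schedule twice-weekly patient falls between 3 − 3 = 0 and 4 + 3 = 7 days. An on-schedule weekly patient falls between 4 and 10 days.

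**Effect on the result (illustration only).** The documents give neither the share affected, *f*, nor the share of the effect that remains, *r*. The mean change is multiplied by 1 − *f*(1 − *r*). Assuming *f* = 10-40% and *r* = 0-50%, the shrinkage runs from 0.10 × 0.50 = 5% to 0.40 × 1 = 40%. The gene count is also sensitive: if half the change is lost, a gene needs an initial change of 0.2 / 0.5 = 0.4 to stay above the 0.2 threshold.

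**How often.** At an assumed rate of 10%, the chance that at least one pair is affected is 1 − 0.9^16 = 82% with 16 patients and 1 − 0.9^22 = 90% with 22. The expected number is 1.6 or 2.2 patients. At 40% it is 6.4 or 8.8.

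**The case against.** A reader might infer several stronger conclusions that the documents do not support.

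- **That every patient with a hold is sampled late.** A hold that resolves before day 21, with azacitidine restarted and cycle 2 on time, leaves the planned interval unchanged.
- **That affected samples are taken after re-methylation, or that pairs beyond 7 days are uninformative.** The 3-7 days is gene reactivation in cell lines after one dose, from unpublished work. The re-methylation statement concerns a different schedule with three weeks off drug. No time course is given for CD138+ or CD34+ cells in treated patients, so intervals of 8-20 days may mean partial loss or none.
- **That the patients with most toxicity are those with the greatest azacitidine effect.** Section 3.3 suggests that cytotoxic concentrations could limit reactivation, and 3.1.3 lists cytopenias for lenalidomide as well. Interval and toxicity are linked by the rules; toxicity and true demethylation are not shown to be.

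Other mitigating points are fair. Sections 5.7.4 and 5.7.5 allow G-CSF and platelet transfusions, which should reduce holds and delays. All drug administration is recorded (5.6.2.2), so the interval can be derived afterwards. Weekly cycle 1 blood samples give DNMT1 data independent of cycle 2. The endpoint is descriptive, with no test or success threshold.

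These points limit the size of the problem without removing it. Nothing in 5.5.4 commits the analysis to using the interval, and DNMT1 in buffy coat does not replace methylation in purified marrow cells. The two timing statements still diverge whenever cycle 2 is late.

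**Conclusion.** The concern holds in a limited form. The endpoint text and the procedure agree only when cycle 2 starts on time. Full twice-weekly dosing gives 3-4 days on time and 24-25 days after the longest delay. Omission of azacitidine to the end of cycle 1 lengthens the interval independently. In those patients the pharmacodynamic measurement may follow partial or full re-methylation, and any resulting error is toward no effect.

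The interval arithmetic rests only on the protocol's dosing days and delay limit. The direction of the error rests on the protocol's own statement about re-methylation, carried over from another schedule. How many patients are affected, and how much signal each loses, cannot be determined from the documents; the percentages above are assumptions. Dose finding, sample size and the clinical endpoints are not touched.

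**What to change.** 1. **Timing.** In 5.5.2 and the Section 2 schedule, set the second research marrow at the end of cycle 1 (study day 29, with the existing ±3 days) whether or not cycle 2 starts that day, for patients still on study. Keep the condition that it precedes any cycle 2 drug. This agrees with 4.2.2 and removes the effect of delay: a fully dosed twice-weekly patient stays at 3-4 days, or 0-7 with the window.
2. **Reporting.** In 5.5.4, report for each pair the days since the last azacitidine dose and the cycle 1 doses received, taken from administration records. This is needed because a fixed date does not cure omitted doses: a last dose on day 11 still gives 18 days.
3. **Analysis.** Keep all pairs in the main analysis, because restricting it to short intervals would itself select on toxicity. Add a prespecified sensitivity analysis limited to short drug-free intervals, for example within 7 days for twice-weekly dosing and up to 10 days for weekly dosing, so that patients treated on schedule are not excluded.

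The cost is protocol wording and a derived variable. In delayed patients the marrow no longer coincides with the cycle 2 start visit. A few patients who never start cycle 2 would have an additional marrow, the one the endpoint text already calls for. No change to dosing or hold rules is implied.
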